6.3 Concomitant Therapy

Throughout the study, investigators may prescribe any concomitant medications or treatments deemed necessary to provide adequate supportive care except for those listed in Section 6.6. Key concomitant therapies are to be collected from informed consent through the end of study. Collect the therapy name, indication, dose, unit, frequency, and start and stop dates and record in the applicable eCRF (See Section 7.2.6).

6.4 Hepatotoxicity Stopping and Rechallenge Rules

Subjects with abnormal hepatic laboratory values (eg, alkaline phosphatase, aspartate aminotransferase [AST], alanine transaminase [ALT], total bilirubin or international normalized ratio [INR]) or signs/symptoms of hepatitis may meet the criteria for withholding of investigational product or other protocol-required therapies. Withholding is either permanent or conditional depending upon the clinical circumstances discussed below (as specified in the Guidance for Industry Drug-Induced Liver Injury: Premarketing Clinical Evaluation, July 2009).

6.4.1 Criteria for Permanent Withholding of Amgen Investigational Product due to Potential Hepatotoxicity

Amgen investigational product should be discontinued permanently and the subject should be followed according to the recommendations in Appendix A (Additional Safety Assessment Information) for possible drug-induced liver injury (DILI), if all the following criteria are met:

| Product: Darbepoetin alfa | | |
|---------------------------|--|--|
| Protocol Number: 20130113 | | |
| Date: 15 April 2013 | | |

Page 30 of 66

- total bilirubin > 2x upper limit of normal (ULN) or INR > 1.5
- increased AST or ALT from the relevant baseline value as specified below:

| Baseline AST or ALT value | AST or ALT elevation |
|---------------------------|----------------------|
| < ULN | > 3x ULN |

- and no other cause for the combination of laboratory abnormalities is immediately apparent; important potential causes for abnormal AST/ALT or total bilirubin values include, but are not limited to:
 - Obstructive gall bladder or bile duct disease
 - Viral or alcoholic hepatitis (eg, Hepatitis A/B/C/D/E, Epstein-Barr Virus, cytomegalovirus, Herpes Simplex Virus, Varicella, etc)
 - Hypoxic or ischemic hepatopathy or congestive hepatopathy in association with significant right sided heart failure
 - Concomitant administration of other hepatotoxins, including drugs that inhibit bilirubin glucuronidation (eg, indinavir, atazanavir, irinotecan) or herbal or dietary supplements
 - Heritable disorders causing impaired glucuronidation (eg, Gilbert's Syndrome); alpha-one antitrypsin deficiency
 - Autoimmune hepatitis
 - Nonalcoholic Steatohepatitis (NASH) or other "fatty liver disease"

If an alternative cause for hepatotoxicity is identified or less stringent conditions developed than what is noted above, determine if investigational product should be permanently or temporarily discontinued based on patient population and/or severity of the hepatotoxicity or event, as deemed appropriate for the safety of the subject.

6.4.2 Criteria for Conditional Withholding of Amgen Investigational Product due to Potential Hepatotoxicity

For subjects that do not meet the criteria for permanent withholding of investigational product outlined above, Amgen investigational product should be withheld if any of the following criteria are met and the subject should be evaluated for DILI:

| Baseline AST or ALT value | AST or ALT elevation |
|------------------------------|--|
| Any | > 8x ULN at any time |
| Any | > 5x ULN but < 8x ULN for \ge 2 weeks |
| Any | > 5x ULN but < 8x ULN and unable to adhere to enhanced monitoring schedule |

• Elevation of either AST or ALT according to the following schedule:

| Product: Darbepoetin alfa | |
|---------------------------|---------------|
| Protocol Number: 20130113 | |
| Date: 15 April 2013 | Page 31 of 66 |

- clinical signs or symptoms that are, in the opinion of the Investigator, consistent with hepatitis (such as right upper quadrant pain/tenderness, fever, nausea, vomiting, jaundice, rash or eosinophilia > 5%). If such signs or symptoms are coupled with ALT or AST elevations > 3x ULN, investigational product should be withheld, or
- total bilirubin > 3x ULN at any time
- alkaline phosphatase > 8x ULN at any time

Amgen investigational product should be withheld pending investigation into alternative causes of DILI. If investigational product is withheld, the subject should be followed according to recommendations in Appendix A for possible DILI. Rechallenge may be considered if an alternative cause, such as acute Hepatitis B infection, is discovered and the laboratory abnormalities resolve to normal or baseline (Section 6.4.3).

6.4.3 Criteria for Rechallenge of Amgen Investigational Product After Potential Hepatotoxicity

The decision to rechallenge the subject should be discussed and agreed upon unanimously by the subject, Investigator, and Amgen.

If signs or symptoms recur with rechallenge, then Amgen investigational product should be permanently discontinued. Subjects who clearly meet the criteria for permanent discontinuation (as described in Section 6.4.1) should never be rechallenged.

6.5 Product Complaints

A product complaint is any written, electronic or oral communication that alleges deficiencies related to the identity, quality, durability, reliability, safety, effectiveness, or performance of any investigational or non-investigational product(s) or device(s).

Any product complaint(s) associated with an investigational product(s) or non-investigational product(s) or device(s) supplied by Amgen are to be reported according to the instructions provided in the IPIM.

6.6 Excluded Treatments or Procedures During the Treatment Period

During the treatment period, subjects should not receive any investigational agents/devices not currently approved by the country's regulatory authority for any indication. Subjects also should not receive thrombopoiesis-stimulating factors (eg, eltrombopag, romiplostim). No other medications are prohibited during treatment period.

Page 32 of 66

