modify the course of the disease by reversing MDS-related cytopenias in some low-risk MDS patients with deletions of the long arm of chromosome 5 (5q-) (List et al, 2005). Transfusions (RBCs and platelets) and antibiotics are ancillary measures in the care of these patients that transiently address deleterious side effects of the cytopenias.

| Class of Intervention | Fyompleo |
|-----------------------------------|--|
| Class of Intervention | Examples |
| Haematopoietic growth factors | ESAs, G-CSF, thrombopoietic growth factors |
| Transcriptional modifying therapy | Hypomethylating agents: 5-azacytidine, decitabine histone deacetylase inhibitors (investigational) |
| Immunomodulating agents | Lenalidomide, thalidomide, anti-thymocyte globulin, cyclosporin A |
| Intensive chemotherapy | Anthracyclines, cytosine arabinoside |
| Cure | Allogeneic stem cell transplantation |

Table 3. MDS Treatments Used in Clinical Practice

ESAs = erythropoiesis-stimulating agents; G-CSF = granulocyte colony stimulating factor Note: These treatments might not have local regulatory approval for use in patients with MDS

Transfusion

Although new therapeutic treatments have shown promise in the treatment of MDS, supportive care remains the primary treatment option for patients with early stage disease (Hofmann and Koeffler, 2005). Transfusions augment the end-product cells in the circulation and are the basic foundation for supportive therapies that buttress the failing erythron, which is the fundamental disease process. Unfortunately, blood product transfusions carry potential undesirable complications including risk of infection with viral agents such as hepatitis and human immunodeficiency virus (Barbara, 2004), acute haemolytic transfusion reactions with potential serious sequelae (Sloop and Friedberg, 1995), transfusion-related acute lung injury (Looney et al, 2004), allergic reactions (Gilstad, 2003), iron overload (Franchini and Veneri, 2004) as well as hypervolemia-related exacerbation of congestive heart failure symptoms (Freudenberger and Carson, 2003). Over time, alloimmunisation impairs the efficacy of blood component transfusions, eventually rendering some patients completely refractory to the intervention. In the MDS setting, increasing rates of RBC transfusions further

(Cheson et al, 2006).

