3. EXPERIMENTAL PLAN

3.1 Study Design

This is a phase 3b, multi-center, open-label, single-arm companion study to the phase 3 MDS 20090160 study for the treatment of anaemic subjects with MDS. Subjects that complete the active-treatment period of the darbepoetin alfa MDS 20090160 study and meet the eligibility criteria may be enrolled into this study to continue treatment of darbepoetin alfa for up to 73 weeks or until lack of response to IP, diagnosis of new malignancy, or progression to AML, whichever occurs first. The overall study design is described by a study schema at the end of the protocol synopsis section.

The study endpoints are defined in Section 10.1.1.

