4. SUBJECT ELIGIBILITY

Investigators will be expected to maintain a screening log of all potential study candidates that includes limited information about the potential candidate (eg, date of screening). This log may be completed and updated via an Interactive Voice Response (IVR)/Interactive Web Response (IWR) system. Before any study-specific procedure, the appropriate written informed consent must be obtained (see Section 11.1).

| 4.1 | Inclusion Criteria |
|-------|---|
| 4.1.1 | General |
| 101 | Subject or subject's legally acceptable representative has provided informed consent prior to any study-specific activities/procedures being initiated; |
| 102 | Subject must continue LTFU within parent study (20090160); |
| 103 | Subject understands that darbepoetin alfa treatment will not be provided by Amgen past week 73; |
| 104 | Subject completes dosing in the active treatment period (through week 70 or week 71) and completed the end of the active treatment period (EOATP) visit of the parent study (20090160); |
| 4.1.2 | Disease-related |
| 105 | Subject must have an ongoing clinically relevant erythroid response as assessed by the Investigator using current response criteria (ie, IWG response criteria); |

Page 25 of 66

| | Darbepoetin alfa Jumber: 20130113 April 2013 Page 26 of 66 |
|-------|--|
| 4.2 | Exclusion Criteria |
| 4.2.1 | Disease-related |
| 201 | Transfusion dependence defined as receiving a total of ≥ 4 units of RBC transfusion in the previous 8-week period prior to enrolment; |
| 202 | Known diagnosis of acute myelogenous leukemia (AML) or marrow collagen fibrosis; |
| 203 | Known refractory anaemia with excess blast-2 (RAEB-2); |
| 204 | Known diagnosis of intermediate-2 or high risk MDS per IPSS; |
| 4.2.2 | Medications or Other Treatments |
| 205 | Subjects received thrombopoiesis-stimulating factors (eg, eltrombopag, romiplostim) in the MDS 20090160 study or planning to receive such agents during the study; |
| 206 | Subjects receiving any investigational agents/devices not currently approved by the country's regulatory authority for the indication of use. |

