6.2.1.2 Dosage Adjustments, Delays, Rules for Withholding or Restarting, Permanent Discontinuation

There will be no interactive voice recognition system (IVRS) guidance for IP dosing in this protocol. The IVRS will only be used in this study to track IP supply to sites and will allocate a IP box number based on the IP dose information entered by the site.

Each subject entering the study will continue the last IP dose and frequency from the parent study (20090160). The investigator may choose to increase the dose of darbepoetin alfa with the maximum dose permitted of 500 µg Q2W. Dose increases should follow a step-wise approach, (eg, 300 µg to 500 µg; 200 µg to 300 µg) with at least 8 weeks at a given dose before the dose may be increased.

The frequency of darbepoetin alfa administration may also be changed, eg, from Q2W to Q3W dosing. No two Q3W or Q2W doses should be administered within any contiguous 14-day or 7-day period, respectively.

The Investigators should use their clinical judgment to assess the best dose and frequency considering risks and benefits, and subject needs. Adjustments to the darbepoetin alfa dose should be made based on the most recent local hemoglobin (Hb) value obtained within 1 day before the dosing visit. Dosing information and local Hb values will be recorded in the eCRF. The reason for a dose change is to be recorded on the eCRF.

Investigators should closely monitor each subjects' Hb values and suspend the dose of IP when the Hb exceeds the 12 g/dL threshold. IP should temporarily be withheld until Hb falls to ≤ 11.0 g/dL at which time IP may be restarted at a dose that is reduced from the previous dose (ie, 500 µg to 300 µg; 300 µg to 200 µg; 200 µg to 100 µg. Table 4 provides an outline of the recommended dose reductions.

Subjects will be permanently discontinued from darbepoetin alfa treatment and will complete the EOS visit at the next scheduled study visit if at any time the:

- subject loses erythroid response defined as Hb decrease of ≥ 1 g/dL compared to day 1 (Hb averaged over 8 weeks)
- subject becomes transfusion dependent defined as ≥ 4 units of RBC transfusion relative to previous 8 weeks prior to enrolment

| Dose | No Previous Dose Reduction | 1 Previous Dose Reduction | 2 Previous Dose Reductions | 3 Previous Dose Reductions |
|---------------|--|--|--|----------------------------------|

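### Section 6.6 allows a second ESA alongside study darbepoetin alfa, and investigational agents that exclusion 206 bars at entry (minor; a cheap wording fix)

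*Protocol*

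**What the plan says.** Protocol Section 6.6 names two things that subjects should not receive during treatment: thrombopoiesis-stimulating factors, and "investigational agents/devices not currently approved by the country's regulatory authority for any indication". It closes the list with "No other medications are prohibited during treatment period". Section 6.3 lets investigators prescribe any supportive care they judge necessary, apart from what Section 6.6 lists.

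Exclusion 206 (Section 4.2.2) uses a different approval test at entry: "Subjects receiving any investigational agents/devices not currently approved by the country's regulatory authority for the indication of use".

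Section 3.1 continues darbepoetin alfa "for up to 73 weeks or until lack of response to IP", or until new malignancy or AML. Section 6.2.1.2 turns lack of response into two mandatory stops. One is transfusion dependence (4 or more RBC units). The other applies if "subject loses erythroid response defined as Hb decrease of ≥ 1 g/dL compared to day 1 (Hb averaged over 8 weeks" is met. Neither refers to other drugs. The same section sets the dose limit ("The investigator may choose to increase the dose of darbepoetin alfa with the maximum dose permitted of 500" µg Q2W) and tells investigators to "suspend the dose of IP when the Hb exceeds the 12 g/dL threshold".

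**The concern.** The dosing safeguards in Section 6.2.1.2 are written for study darbepoetin alfa alone. A second ESA acts on the same erythroid target, yet no maximum dose, step-up rule or haemoglobin hold in this protocol applies to it. If it raises haemoglobin, the measured fall from day 1 no longer reflects response to study drug. A subject who has lost that response could then stay on study drug as late as week 73. The objective in Section 1 is access for subjects who continue to benefit, and the protocol checks for thrombovascular events at every visit, so exposure without benefit matters for safety.

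The mismatch with exclusion 206 is separate and simpler: the same investigational agent can make a subject ineligible on one day and be allowed on the next. The note to Table 3 shows that this is not an empty class. It says of MDS treatments, including ESAs and hypomethylating agents: "These treatments might not have local regulatory approval for use in patients with MDS".

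No hypothesis test or efficacy endpoint is at stake. The effect is on when study drug must stop and on attribution of adverse events. The listings planned in SAP Section 5 include transfusions and haemoglobin at enrolment, but neither concomitant medication nor on-study haemoglobin, so they would not show the problem.

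**Working it through.** The plan gives no figure to reproduce. The check is a comparison of the rules, then an illustration of how far the stop can be masked.

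**Rules compared**

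| Agent | At entry | During treatment (6.6) |
|---|---|---|
| Investigational, no approval anywhere in the country's system | barred (206) | barred |
| Investigational, approved only for another indication | barred (206) | allowed |
| Second ESA given as ordinary care | not addressed | allowed |
| Thrombopoiesis-stimulating factor | barred (205) | barred |

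**Threshold**

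Let L be the darbepoetin alfa effect lost and g the gain from a second drug, with additive effects (an assumption). The haemoglobin stop is met when L − g ≥ 1.0, that is L ≥ 1.0 + g.

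- g = 0: L ≥ 1.0 g/dL
- g = 0.5: L ≥ 1.5 g/dL
- g = 1.0: L ≥ 2.0 g/dL
- g = 1.5: L ≥ 2.5 g/dL

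The minimum IWG haemoglobin response in Section 2.1 is 1.5 g/dL. Its complete loss (L = 1.5) gives a net fall of 1.5 − g, which is below the threshold once g exceeds 0.5.

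**Chance that the stop fires**

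Inputs:
- Day 1 haemoglobin is a single value (Study Glossary).
- Visits are Q3W, so an 8-week average holds 3 values.
- Within-subject SD s = 0.5 g/dL is an assumption, with range 0.3 to 1.0.
- Loss is complete from week 25, and g is present from then on (assumptions).

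*One window.* The SD of the 8-week mean minus day 1 is s√(1 + 1/3), which is 0.577 for s = 0.5. P(fire) = Φ((1.5 − g − 1.0)/0.577):
- g = 0: Φ(0.866) = 81%
- g = 1.0: Φ(−0.866) = 19%
- g = 1.5: Φ(−1.732) = 4%

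*All windows.* Section 6.2.1.2 applies the stop at any time, so one window is not enough. Visits at weeks 25, 28, …, 73 number (73 − 25)/3 + 1 = 17, which gives 15 rolling windows of 3 values. All windows share the same day 1 error. A simulation of 1,000,000 subjects per cell gives the chance of firing at least once:

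| s (g/dL) | g = 0 | g = 1.0 | g = 1.5 |
|---|---|---|---|
| 0.3 | 99% | 23% | 1% |
| 0.5 | 96% | 45% | 15% |
| 1.0 | 90% | 64% | 45% |

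At g = 1.5 the net fall is zero, so those firings are measurement noise. They equal the rate in a subject who has lost nothing.

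**Extra exposure if the stop never fires**

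With loss at week 25, a full 8-week window is available at about week 33. Doses after that, at an assumed constant 500 µg:
- Q3W, weeks 34 to 73: (73 − 34)/3 + 1 = 14 doses, 7,000 µg
- Q2W, weeks 35 to 73: (73 − 35)/2 + 1 = 20 doses, 10,000 µg

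These are upper limits for this scenario.

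**The case against.** Section 6.6 is an explicit choice in an access study, and other controls exist. Section 3.1 itself ends treatment at lack of response. Section 6.2.1.2 asks investigators to weigh risk and benefit, and Section 8.2 lets them withdraw study drug at any time. If a second ESA pushes haemoglobin above 12 g/dL, study drug is held and restarted at a lower dose, and a fourth reduction ends it. Entry requires an ongoing response, and the second drug must start before the 8-week average has fallen by 1 g/dL. It may also add little: in one Appendix E study of 15 previously ESA-treated patients, only 3 (20%) responded to darbepoetin alfa, with pegfilgrastim added for nonresponders. All of this stands, and it makes the event unlikely. It does not close the gap, because discretion is not the mandatory stop that the sponsor wrote, and the hold does nothing while haemoglobin sits below 12 g/dL.

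Three stronger readings are tempting and are not supported.
- *The protocol expects a second ESA, because Section 7.2.6 records any ESA.* The same list records non-protocol doses of study drug, which are departures from the plan. It is data capture, not expected use.
- *The stop is disabled.* It is weakened. A single-window calculation (19% and 4%) exaggerates the loss, because the rule is applied repeatedly.
- *Starting lenalidomide, azacitidine or a similar drug should end study drug.* That is the sponsor's choice. It could take study drug from a subject who still benefits, against the access objective, and G-CSF and transfusions below 4 units would still support haemoglobin.

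**Conclusion.** The point holds in two parts. Section 6.6 permits a second ESA that the dose maximum and the haemoglobin hold do not cover and that can mask the haemoglobin-based stop. It also permits investigational agents approved only for another indication, which exclusion 206 bars at entry. Both follow from the wording alone.

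The size of the masking rests on assumptions: additive effects, complete loss of a 1.5 g/dL response, the within-subject SD, and a gain g that the documents do not give. The direction does not depend on the SD chosen. Under the central case, the chance that the stop ever fires drops from about 96% to 45% or 15%. SAP Section 4.1.2 projects fewer than 10 subjects from one country, and the number affected may be 0. This is a minor point, worth fixing because the fix is nearly free.

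**What to change.** Make two edits to Section 6.6.

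1. Add to the excluded treatments: *any ESA other than study darbepoetin alfa*.
2. Replace the approval test *for any indication* with the one in exclusion 206, *for the indication of use*, so that entry and treatment follow one rule.

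No new data, visits or analyses are needed. The cost is slightly less prescribing freedom during treatment. The second edit should keep the word *investigational*, so that it is not read as a ban on ordinary off-label care. Whether starting a disease-modifying MDS drug should also end study drug is left to the sponsor.

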7. STUDY PROCEDURES

7.1 Schedule of Assessments

| | Screen / Enroll | Active Treatment Period | End of Study ^g |
|--|---------------------------------|---|------------------------------|
| Study Week | 72 / 73 ^a / Day 1 | Q3W or Q2W dosing up to week 73 (Q3W) | 76 |
| Informed Consent | x | | |
| Medical history | x | | |
| Physical examination | x | | |
| Physical measurements (height and weight) ^b | x | performed at each visit | x |
| Vital Signs (heart rate, temperature, blood pressure) | х | performed at each visit | x |
| Assess for signs and symptoms of clinically relevant TVE | x | performed at each visit | x |
| Adverse Events (AEs), Serious Adverse Events (SAEs) ^C | x | performed at each visit | x |
| Key concominant medications, and red blood cell (RBC) transfusions | x | Assessed at each visit and throughout the study | |
| Local laboratory haemoglobin for dosing decision | x | performed at each visit | |
| IP (darbepoetin alfa) administration ^e | х | performed at each visit | |
| Darbepoetin alfa antibody sample collection | x ^f | | х |

Table 5. Schedule of Assessments

a. Last visit of the MDS 20090160 study at week 72 / 73 is the first dosing visit for 20130113.

b. Height only collected as part of screening. Weight collected at each visit.

c. AEs and SAEs will be reported throughout the study through 30 days after last dose of IP (darbepoetin alfa).

d. Dosing will occur Q3W ± 6 day or Q2W ± 6 days. No 2 Q3W or Q2W doses should be administered within any contiguous 14-day or 7-day period, respectively. Dosing decision based on local lab Hb taken within 1 day before IP dosing visit (See Protocol Section 6.2.1.2 for dosing guidelines).

e. Results of local laboratory Hb must be available and reviewed prior to IP adminstration.

f. A Day 1 antibody sample is not required if appropriately collected in the MDS 20090160 study at the End of the Active Treatment Period (EOATP) visit.

g. End of Study (EOS) visit at week 76 or 3 weeks after last dose of IP from Q3W or Q2W dosing for subjects that end IP early.

Page 33

